#### Secondary client outcomes:

- Knowledge about health services and health behaviours
- Agency to make decisions about health
- Self-esteem
- Well-being

Knowledge, agency and self-esteem will be measured using questions from existing tools or using new locally-specific questions that will be developed and validated during Phase 1.

The following definition of adolescent well-being has been proposed 'Adolescents thrive and are able to achieve their full potential'.  In Phase 1, the development of a tool to measure wellbeing will build on extensive previous work led by study team member [name] on adapting, developing and testing wellbeing measures for use in economic evaluations of complex interventions in Malawi, Mozambique and Uganda. 

- Reported health-related risk and protective behaviours (see Appendix 1)
- Reported engagement with health services

Reported use of health services will be measured in the past 4 months and in the past 12 months. Use of health services in the past 12 months by 10-24 year olds is proposed as an indicator for monitoring adolescent health worldwide.

- Clinical outcomes (see Appendix 1)
- Educational outcomes

School attendance and attainment in the year prior to and after the initial Y-Check visit will be captured through a review of school registers and/or self-reported by participants during visits. In Phase 1 we will explore the feasibility of measuring cognitive skills and ability, for example through a standardised reading test or computer based tasks of verbal and visuo-spatial working memory.

• Client-centered outcomes (to be defined during Phase 1- see section 2.3)

# 6.2 Sample size calculations

The package will be delivered to 2000 adolescents (500 per gender in each age group), however, the primary outcome is only measured among those who screen positive for at least one condition. Within one age group and gender, if 150 (30%) of 500 participants screen positive for at least one condition, and 75% of those who screen positive are correctly managed (n=112; primary outcome), the 95%CI for correct management will be  $\pm 1.7\%$ .

The sample size also allows us to describe prevalence of individual conditions, and proportion with corrective action taken (secondary outcomes). For example, if 50 of 1000 participants in one age group

(5%) screen positive for a given condition, and 75% of these have complete referral, the 95%CI will be 62%-87%, or a 95%CI of 35%-65% if 50% complete referral.

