## **Prospective Intervention study**

We will follow the STROBE guidelines for the reporting of cohort studies. We will create a flowchart showing the number of communities and schools and the number of participants per community and school at each contact point in the cohort study. We will use descriptive analysis to compare the community-level and school-level characteristics of the four study communities and schools.

The primary outcome is a single proportion which will be presented with a 95% confidence interval for each of the 4 target populations: 10-13y male, 10-13y female, 16-19y male, 16-19y female. Secondary outcomes which are measured at a single time point will be presented in a similar way. For outcomes which are measured at two or more time-points, a before-after analysis will be conducted comparing differences in measures between the two time-points. The unit of analysis will be the individual. For clinical outcomes which are measured at two or more time-points, the initial check-up visit (baseline) will give the prevalence of undiagnosed and untreated chronic conditions which will represent the counterfactual. The proportion of undiagnosed and untreated chronic conditions at the 4-month follow-up visit will be formally compared to this counterfactual to estimate the effectiveness of the intervention in improving these clinical outcomes. We will assess health service and client determinants of correct management of conditions at 4 months using multivariable regression.

**Digital platform data** De-identified data on information viewed, games played, rewards provided/used along with programmatic data on behaviours and clinical conditions etc. will be analysed using machine learning approaches to understand the sub-groups/segments of adolescents who participate in Y-Check. This analysis will help us to define, develop, and pilot test targeted messaging for different sub-groups of young people who attend Y-Check follow-up visits. We will also analyse this data to develop algorithms which could potentially be used in the future phases of the Y-Check programme to further personalise the Y-Check user experience to maximise relevance, uptake and retention.

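### The only precision figure given for the primary outcome, ±1.7%, is wrong: 75% of 150 gives about ±6.9 percentage points, four times wider.

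*Protocol*

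**What the plan says.** Section 6.2 takes the study size as given: "The package will be delivered to 2000 adolescents (500 per gender in each age group"). It notes that "the primary outcome is only measured among those who screen positive for at least one condition", and then works an example for a single stratum of 500 in which 30%, or 150 adolescents, are screen-positive. For that stratum the protocol supposes that "75% of those who screen positive are correctly managed (n=112; primary outcome), the 95%CI for correct management will be", and the value it then gives is a half-width of ±1.7%.

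The next paragraph of section 6.2 turns to secondary outcomes. With 50 screen-positives in one age group, if "75% of these have complete referral, the 95%CI will be 62%-87%, or a 95%CI of 35%-65% if 50% complete referral".

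Section 6.3 (Prospective Intervention study) sets out the primary analysis: "The primary outcome is a single proportion which will be presented with a 95% confidence interval for each of the 4 target populations". The stratum of about 150 screen-positives is therefore the denominator that applies to the reported result. No other precision figure for the primary outcome appears in the protocol.

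**The concern.** The two examples in section 6.2 cannot both be right. At the same assumed proportion of 75%, 50 people are given an interval about 25 points wide, while 150 people are given one only 3.4 points wide. Tripling a sample narrows an interval by a factor of about 1.7, not 7.

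The study has no control arm, and the primary outcome is not tested against a threshold. The width of the interval is therefore what tells a reader how much the primary analysis can deliver. An ethics committee, a funder or the Scientific Advisory Committee reading section 6.2 would expect each group's result to be known to within about 73% to 77%. One stated objective (section 2.2, objective 2.v) is to obtain parameters for planning a larger evaluation, so an overstated precision could also be carried into that later design.

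**Working it through.** **Inputs, all from section 6.2:** n = 150 screen-positives in one age-by-gender group (30% of 500); p = 0.75; 95% confidence. The count of 112 is 75% of 150 (112.5) rounded down.

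**Stated figure:** ±1.7 percentage points.

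**Recalculation (normal approximation):**
- Standard error = sqrt(0.75 × 0.25 / 150) = 0.0354, or 3.5 points.
- Half-width = 1.96 × 0.0354 = 0.0693, or 6.9 points.
- Interval = 68.1% to 81.9%.
- Ratio to the stated figure = 6.93 / 1.7 = 4.1.

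**Other interval methods, using 112/150:** Wald 67.7% to 81.6%; Wilson 67.2% to 81.0%; exact (Clopper-Pearson) 66.9% to 81.4%. The half-width is about 7 points in each case.

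**Attempts to reproduce ±1.7 by another route:**

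| Variant (p = 0.75) | Half-width, points |
|---|---|
| n = 150, continuity-corrected | 7.3 |
| n = 150, 90% interval | 5.8 |
| n = 150, finite population correction (150 of 500) | 5.8 |
| n = 112 | 8.0 |
| n = 300 (one age group) | 4.9 |
| n = 500 | 3.8 |
| n = 600 (all four groups pooled) | 3.5 |
| n = 1,000 | 2.7 |
| n = 2,000 (everyone screen-positive, pooled) | 1.9 |

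None gives 1.7. The nearest value found is one standard error with 600 pooled screen-positives, sqrt(0.1875 / 600) = 1.77 points, which is neither a 95% interval nor a single group.

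**Sample that ±1.7 would need:** 0.75 × 0.25 × (1.96 / 0.017)² = 2,492 screen-positives per group.

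**Check against the protocol's other precision figures:**
- 50 screen-positives, 75%: the exact interval for 38/50 is 61.8% to 86.9%, against a stated 62% to 87%.
- 50 screen-positives, 50%: the exact interval for 25/50 is 35.5% to 64.5%, against a stated 35% to 65%.
- Section 3.7.2 (Schistosomiasis), n = 200 at 15% prevalence: 1.96 × sqrt(0.15 × 0.85 / 200) = 4.9 points, against a stated 5%.
- Scaling the first of these: a half-width of 12.5 points at n = 50 becomes 12.5 / sqrt(3) = 7.2 points at n = 150.

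The other figures agree with their inputs to within rounding. Only the primary-outcome figure does not.

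**The case against.** The arithmetic is not in dispute; the objections concern how much follows from it.

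- **The sample size was not derived from ±1.7%.** Section 6.2 starts from 2,000, sets no precision target, and also gives secondary-outcome intervals that are about right. This stands. The error misstates the precision; it does not by itself show that the study is too small.
- **The protocol makes no claim to distinguish the four groups.** Section 6.3 presents an interval for each and plans no between-group test of the primary outcome. This also stands. A reader might infer such discrimination from ±1.7%, but the text does not promise it, so a restatement of resolvable differences is optional.
- **The 30% positivity is hypothetical.** Appendix 1 lists many conditions that could make someone screen-positive, so the true share may be higher. Assuming 30% to 90% of 500, n runs from 150 to 450 and the half-width from 6.9 to 4.0 points. Even at 100% it is 3.8 points, so the objection does not rescue 1.7.
- **A Wald figure would sit beside what looks like an exact interval** in the same section. The difference is about one point. It is a reason to name the method, not to keep the figure.
- **The figure may have been misread from the PDF.** Nothing points to this, and the source can be checked at once.

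**Conclusion.** The figure is wrong as written. On the protocol's own inputs the 95% half-width for the primary outcome in one age-by-gender group is about 6.9 percentage points, not 1.7, so the stated precision is overstated about fourfold. No standard interval method tried, and no denominator up to all 2,000 participants, yields the stated value.

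The 6.9 points rest on 150 screen-positives, 75% correctly managed, and independent participants. Recruitment is through schools and community hubs, and positive clustering would widen the interval. Taking design effects purely as assumptions, 1.5 would give ±8.5 points and 2.0 would give ±9.8.

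The correction should be made because this is the only precision statement for the primary outcome and the error is in the favourable direction. It changes neither the endpoint nor the planned analysis, and it implies no increase in sample size.

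**What to change.** In section 6.2, replace ±1.7% with: ±6.9 percentage points (95% CI approximately 68% to 82%, normal approximation, before any allowance for clustering). If the authors prefer to match the apparently exact secondary-outcome intervals, give 67% to 81% for 112 of 150 and name the method.

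Optionally, add a line showing how the half-width changes with the share who screen positive, since 30% is only an example.

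The cost is one corrected figure and a short qualifier. No participants, procedures or analyses change; the stated precision becomes less favourable.

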# 6.3 Statistical analysis

#### **Crowdsourcing contest**

Contest metrics (e.g. number and type of entries) will be described according to the sociodemographic characteristic of participants.

#### Validation study

Data will be analysed using appropriate statistics to calculate the following measures (dependant on method of validation used): sensitivity, specificity, positive predictive value, negative predictive value.

#### **Programmatic data**

Quantitative programmatic data including screening tests results, services delivered, and referrals made will be described according to age, sex, and location.

## **Prospective Intervention study**

We will follow the STROBE guidelines for the reporting of cohort studies. We will create a flowchart showing the number of communities and schools and the number of participants per community and school at each contact point in the cohort study. We will use descriptive analysis to compare the community-level and school-level characteristics of the four study communities and schools.

The primary outcome is a single proportion which will be presented with a 95% confidence interval for each of the 4 target populations: 10-13y male, 10-13y female, 16-19y male, 16-19y female. Secondary outcomes which are measured at a single time point will be presented in a similar way. For outcomes which are measured at two or more time-points, a before-after analysis will be conducted comparing differences in measures between the two time-points. The unit of analysis will be the individual. For clinical outcomes which are measured at two or more time-points, the initial check-up visit (baseline) will give the prevalence of undiagnosed and untreated chronic conditions which will represent the counterfactual. The proportion of undiagnosed and untreated chronic conditions at the 4-month follow-up visit will be formally compared to this counterfactual to estimate the effectiveness of the intervention in improving these clinical outcomes. We will assess health service and client determinants of correct management of conditions at 4 months using multivariable regression.

**Digital platform data** De-identified data on information viewed, games played, rewards provided/used along with programmatic data on behaviours and clinical conditions etc. will be analysed using machine learning approaches to understand the sub-groups/segments of adolescents who participate in Y-Check. This analysis will help us to define, develop, and pilot test targeted messaging for different sub-groups of young people who attend Y-Check follow-up visits. We will also analyse this data to develop algorithms which could potentially be used in the future phases of the Y-Check programme to further personalise the Y-Check user experience to maximise relevance, uptake and retention.

**Mathematical Modelling** Using data from the intervention study, the cost-effectiveness of various check-up visit screening and treatment/referral scenarios will be modelled taking into account the underlying epidemiology, sensitivity and specificity of screening tests, and effectiveness of condition-specific interventions.

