#### Design:

The study comprises: Phase 1: Development and piloting; Phase 2: Implementation and evidence generation; Phase 3: Knowledge dissemination and translation. Outputs will be (i) a novel intervention to improve adolescent health and well-being, (ii) evidence in urban settings in Zimbabwe on the interventions feasibility and cost-effectiveness, (iii) guidelines for implementation and evaluation in Zimbabwe and in other LMICs, and (iv) proposals for follow-on studies in Zimbabwe and other LMICs.

**Intervention:** The Y-Check strategy will involve the screening and treatment/referral of adolescents for important conditions through health check-up visits at two key time points during adolescence: early adolescence (10-14y) and mid/late adolescence (15-19y). Adolescents will only be screened for conditions with an accurate and acceptable screening test and a locally-accessible effective intervention e.g. mental health, HIV, vision, hearing, and anaemia. The package of services will include risk reduction counselling and general health information and counselling.

**Study Outcomes:** In this hybrid effectiveness-implementation study, both implementation process and adolescent outcomes will be captured. The primary outcome will be the proportion of those screening positive for at least one condition who receive appropriate on-the-spot care or complete appropriate referral within 4 months. Secondary outcomes will include yield of previously undiagnosed and un-referred conditions; intervention acceptability, adoption, appropriateness, feasibility, fidelity, and cost; reported health-related risk and protective behaviours; engagement with health services; well-being; clinical and educational outcomes.

**Study population:** The intervention will be delivered to 1000 10-14 year old males and females and 1000 15-19 year old males and females. An initial pilot study of around 200 participants will be conducted before the main intervention, taking the total number of participants to 2200. Parents, carers and other stakeholders (teachers, service providers, community leaders etc.) will participate in study development and evaluation workshops and interviews.

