# 3.7 Check-up visits

The target school grades and age-ranges will be agreed in consultation with MoPSE, MoHCC and other stakeholders during Phase 1 of the study and will align with existing or planned school services. The timing of the check-up visit will be agreed with teaching staff, students, and community stakeholders. Y-Check will target two age cohorts, Y-Check 1 (10-14 year olds) and Y-Check 2 (15-19 year olds).

#### Y-Check 1

The first visit, Y-Check 1, will target the 10-14 year old age cohort and will be delivered exclusively in primary schools as a very high proportion of the target population are attending primary schools (90.5% (MICS 2019). The intervention is likely to target adolescents in Grade 5 where the majority of students are aged 10 years (45% aged 10 years in MICS 2019) or 11 years (21% aged 11 years in MICS 2019). However, as a result of starting school late or repeating years there are a proportion of students who are over age for their grade (10% were aged 12 and 4% were aged 13 years).

#### Y-Check 2

The second check-up visit, Y-Check 2, will target the 15-19 year old age cohort and will take place both in secondary schools and at community venues (16-19 years only in the community). In schools, Y-Check 2 is likely to target adolescents in Form 3 where most learners are aged 15 or 16. School attendance drops off in secondary schools and an estimated 50% of 16 and 17 year olds are out of school. We are therefore proposing to also deliver Y-Check 2 at community venues to adolescents aged 16-17 years who are not attending school. Community venues will be multi-purpose use locations, such as a community centre. Using methods developed to deliver sexual and reproductive health services in the ongoing CHIEDZA trial (www.chiedza.co.zw) we will create bespoke 'hubs' in existing community centres to deliver Y-Check 2. This will be accompanied by mobile outreach at locations frequented by adolescents (e.g. shopping centres, workplaces, bars, sports venues) to advertise the check-up visits and achieve high coverage.

Information about Y-Check services will be shared with parents/guardians and community members before the intervention team visit the school/community venue. Consent procedures will differ for those recruited in schools (Y-Check 1 and Y-Check 2) and those recruited in the community.

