# 4.3 Prospective Intervention study (Phase 2)

In a prospective intervention study, Y-Check will be implemented for 10-14 year olds in up to 6 government primary schools (N=1000), and for 15-19 year olds at up to 8 secondary schools and up to 4 community hubs (N=1000). The Y-Check programme is described in section 3.

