#### 4.3.1 Cohort recruitment and follow-up

Prior to the Y-Check visit, programme participants will be invited to join the research cohort and agree to the following additional activities:

- Self-completion of an additional module of the pre-consultation questionnaire (to measure baseline outcomes not captured for programme participants e.g. knowledge, intention, agency, educational outcomes)
- Observation of check-up visit and referral visit procedures by a Y-Check team member.
- Exit interviews
- Follow up visits at 4-months and 12-months (questionnaire and screening tests)
- Potential participation in qualitative interviews or group activities

Y-Check 1: The information sheet distributed by the school about the check-up visits (section 3.7) will include information about the Y-Check research cohort and the need for separate consent to participate in the research study. Eligible students will be asked to return completed informed parental consent and individual assent forms either before or on the day of the check-up visit.

Eligibility criteria will be:

- Currently enrolled in Grade 5, 6 or 7 in one of the study primary schools
- Adolescent and their parent/guardian have consented/assented to participate in the check-up visit
- Written informed parental/guardian consent and client assent to participate in the research study

Y-Check 2: The information sheet distributed by the school about the check-up visits (section 3.7) will include information about the Y-Check research cohort and the need for separate consent to participate in the research study. Eligible students will be asked to return their completed informed consent form either before or on the day of the check-up visit.

In the community, mobilisation and advertisement will encourage adolescents to attend the community hubs for check-up visits and will describe the accompanying research study. At the community hubs,

following confirmation of eligibility, clients will be asked to provide written informed consent to participate in the research study.

Eligibility criteria will be:

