#### Schools:

- Currently enrolled in Form 3, 4 or 5 in one of the study secondary schools
- Adolescent and their parent/guardian have consented/assented to participate in the check-up visit
- Written informed parental/guardian consent and client assent to participate in the research study Community hub:
- Currently aged 16 to 19 years & resident in the study community
- Adolescent has consented to participate in some or all components of the check-up visit
- Written informed consent from client to participate in the research study

Cohort follow-up visits will be at schools for Y-Check 1 participants, and at the school and/or community hubs for Y-Check 2 participants, using SMS reminders and active follow-up. Follow-up of Y-Check 1 clients may also be done using the contact details provided by parents/carers. Y-Check 2 clients will be asked to provide mobile phone numbers so that they can receive reminders about referrals and a monthly health message during the 12-month follow-up period. USD5 will be given to each participant to cover any transport costs that they might have incurred to attend follow-up visits.

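### Section 6.3 reports the primary outcome for ages 10-13 and 16-19, but the study enrols ages 10-14 and 15-19, so read literally 14- and 15-year-olds fall in no primary-outcome group

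*Protocol*

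**What the plan says.** Section 6.3 (Prospective Intervention study) describes the primary outcome as one proportion with a 95% confidence interval, shown for "each of the 4 target populations: 10-13y male, 10-13y female, 16-19y male, 16-19y female". Secondary outcomes measured once are to be shown likewise. The only other place with these bands is section 1 (Introduction).

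The cohorts are defined differently elsewhere:

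- Executive Summary: "The intervention will be delivered to 1000 10-14 year old males and females and 1000 15-19 year old males and females".
- Section 3.7: "Y-Check will target two age cohorts, Y-Check 1 (10-14 year olds) and Y-Check 2 (15-19 year olds". Sections 2.3, 4.3 and 7.5 use the same bands.
- Section 4.3.1, Y-Check 1 eligibility: "Currently enrolled in Grade 5, 6 or 7 in one of the study primary schools".
- Section 4.3.1, Y-Check 2 eligibility in schools: "Currently enrolled in Form 3, 4 or 5 in one of the study secondary schools".
- Section 4.3.1, Y-Check 2 eligibility at the hubs: "Currently aged 16 to 19 years & resident in the study community".

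On the ages expected in secondary schools, section 3.7 says "Y-Check 2 is likely to target adolescents in Form 3 where most learners are aged 15 or 16".

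**The concern.** The sentence that fixes the primary-outcome groups uses age bands that do not cover the enrolled population. The ages left out are not marginal to recruitment, because 15 is one of the two main ages in the school year that Y-Check 2 is likely to target.

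Any omission would also be selective. The hubs take nobody under 16, so every 15-year-old left out was recruited at school. Section 3.7.2 limits HIV testing, STI testing and the circumcision pathway to the hubs, and section 6.1 counts a participant as a success only if every identified condition is managed. School and hub participants can therefore differ in how many conditions they must have managed. Losing one school age group could change what the Y-Check 2 proportion describes, as well as its precision.

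If the wording stays, the analyst must choose between the stated bands and the enrolled cohorts, possibly after seeing the data.

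**Working it through.** **1. The bands side by side**

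| Source | Younger | Older | Ages 10-19 not covered |
|---|---|---|---|
| Executive Summary; 2.3; 3.7; 4.3 | 10-14 | 15-19 | none |
| 6.3 (and section 1) | 10-13 | 16-19 | 14 and 15 |

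The two definitions differ by exactly ages 14 and 15.

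**2. Can those ages enrol?** Yes. Age 14 lies within the Y-Check 1 range and age 15 within the Y-Check 2 range. The school criteria in 4.3.1 are by grade or form. Age 15 can enter Y-Check 2 only through schools.

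**3. Does anything else in 6.3 include them?** No. It states no pooled primary estimate and no rule for analysing participants as enrolled.

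**4. The plan's own precision figure.** Section 6.2 takes 500 per age-sex group, 150 (30%) screening positive and 75% of those correctly managed, and states ±1.7%. The usual formula gives:

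1.96 × √(0.75 × 0.25 / 150) = 1.96 × 0.0354 = 0.069, that is ±6.9 points.

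The exact interval for 112/150 is 66.9% to 81.4%. The ±1.7% does not follow from its inputs; at 75% it would need about 2,490 screen-positives. That is a separate matter, and ±6.9 is the baseline here.

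**5. Precision if a share s of a group is left out.** The protocol does not give s, so the values below are assumptions. I also assume that the omitted participants screen positive at the same 30%. Then n = 150 × (1 − s), and the half-width is 1.96 × √(0.1875 / n).

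| s (assumed) | Screen-positives | 95% half-width |
|---|---|---|
| 0% | 150 | ±6.9 |
| 4% | 144 | ±7.1 |
| 10% | 135 | ±7.3 |
| 20% | 120 | ±7.7 |
| 30% | 105 | ±8.3 |
| 40% | 90 | ±8.9 |
| 50% | 75 | ±9.8 |

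**6. Shift in the estimate.** Let the omitted share s of screen-positives have success proportion p_o, and those retained p_r. The whole group has (1 − s)p_r + s·p_o, while the reported figure is p_r. The difference is s(p_r − p_o). For each point by which retained and omitted participants differ, the estimate moves by 0.04 points at s = 4% and by 0.5 points at s = 50%. The protocol gives no success rates by venue or age, so neither the size nor the direction of the shift can be stated.

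**The case against.** The strongest reply is that these are outdated labels and not an exclusion rule. Section 6.3 never says that anyone is left out. Sections 4.3.2 and 6.1 define the primary outcome among all who screen positive, with no age limit, and section 6.2 sizes the study on the full 2000. The same bands survive in the Introduction. Sections 2.3 and 3.7 leave the exact grades and ages to be agreed in Phase 1, and a statistical analysis plan that is not at hand may name the groups correctly.

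Much of this stands. A reader might infer that the sponsor means to discard 14- and 15-year-olds; the protocol does not support that. The protocol nevertheless fixes the four groups itself and fixes them inconsistently with its own cohorts. The Phase 1 provision does not reconcile the two sets of bands.

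Three further inferences should be resisted:

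- **That a fifth of Grade 5 is lost.** The shares in section 3.7 for ages 10 to 13 (45%, 21%, 10% and 4%) sum to 80%. The other 20% is not broken down and may include children under 10, who are outside 10-14 as well. The mismatch in Y-Check 1 concerns only 14-year-olds, whose share is not given. The falling series suggests few of them in Grade 5; Grades 6 and 7 are also eligible, without figures.
- **That the planned 500 per sex and age group is not delivered.** Section 6.2 refers to delivery of the package, which the reporting bands in 6.3 do not alter.
- **That school recruitment has no age limit at all.** The criteria in 4.3.1 state none, but section 3.7 labels school recruitment 10-14 and 15-19 years. The position is ambiguous.

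A specific loss for Y-Check 2 would likewise need the school-to-hub split and the age mix across Forms 3 to 5, and the protocol gives neither.

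**Conclusion.** The inconsistency is real and sits in the sentence that defines the primary-outcome groups, so it should be corrected before analysis. Followed as written, it leaves ages 14 and 15 in no group for the primary outcome or for single-time-point secondary outcomes. It bears mainly on school-recruited 15-year-olds in Y-Check 2, and the risk of tilting that estimate towards the hubs matters more than the lost precision.

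The precision cost is small to moderate: from ±6.9 points to between ±7.1 and ±9.8. That range rests on assumed shares of 4% to 50%, on 30% screening positive and on 75% correctly managed. The finding is that the text contradicts itself, not that an exclusion is planned.

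**What to change.** In section 6.3, define the four groups as Y-Check 1 male, Y-Check 1 female, Y-Check 2 male and Y-Check 2 female. State that every participant is analysed in the stream in which they were screened, whatever their exact age, and that single-time-point secondary outcomes use the same groups. Defining the groups by stream is safer than replacing one pair of age bands with another: it keeps pupils who are over or under age for their grade, and it holds whatever age ranges are agreed in Phase 1. Align the age bands in section 1 with the rest of the protocol.

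The cost is a wording change in two places. Sex and school or hub are already recorded at the check-up (Table 3), so no new data and no change to the planned recruitment are needed.
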